7. SAFETY MONITORING

7.1. Adverse Events

Collection of AEs will commence from the time the subject signs the informed consent to participate in the study and continue until the subject discontinues study participation (eg, screen failure, study withdrawal, or study completion [ie, Follow-up Phone Call]).

7.1.1. AE Definition

An AE is the appearance or worsening of any undesirable sign, symptom, or medical condition, even if the event is not considered to be related to study drug. Study drug includes the investigational drug under evaluation during any phase of the study. Medical conditions/diseases present before starting study drug are only considered AEs if they worsen after starting study drug. Abnormal laboratory values or test results constitute AEs only if they induce clinical signs or symptoms, are considered clinically significant, or require therapy.

The occurrence of AEs should be sought by non-directive questioning of the subject at each visit during the study. AEs also may be detected when they are volunteered by the subject during or between visits or through physical examination, laboratory test, or other assessments. All AEs must be recorded on the Adverse Event Form with information regarding the intensity, relationship to study drug (imaging ligand), relationship to study procedures, duration and whether it meets the criteria as a SAE.

The World Health Organization (WHO) toxicity grading scale (see Section 12) will be used for assessing AE severity. Table 2 will be used for assessing severity for AEs that are not specifically listed in the WHO toxicity grading scale.

Table 2: Grading of AEs

Grade	Intensity
1	An AE that is mild and transient (<48 hours). No treatment or therapeutic intervention is required.
2	An AE that is moderate. There is a mild to moderate limitation in activity. Some assistance may be needed. No or minimal therapeutic intervention is required.
3	An AE that is severe. There is a marked limitation in activity, and some assistance is usually required. Medical intervention and/or therapy is required. Hospitalization is possible.
4	An AE that is life-threatening. There is an extreme limitation in activity, and significant assistance is required. Significant medical intervention and/or therapy is required, and hospitalization or hospice care is probable.

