6.4.4.2. Clinical chemistry

A standard chemistry panel will be obtained including electrolytes, liver function tests and analytes to measure renal function, including albumin, albumin/globulin ratio (calculated), alkaline phosphatase, ALT, AST, bun/creatinine ratio (calculated), calcium, carbon dioxide, chloride, creatinine with GFR estimated, globulin (calculated), glucose, potassium, sodium, total bilirubin, total protein, urea nitrogen.

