6.4.5. Electrocardiogram (ECG)

A standard 12 lead ECG will be performed. Interpretation of the tracing must be made by a qualified physician and documented on the ECG section of the case report form (CRF). Each ECG tracing should be labeled with:

- Study number
- Subject NDOB (Name Date of Birth) code
- Subject number
- Date
- Time

All ECG tracings will be kept in the source documents at the study site. Only clinically significant abnormalities will be reported on this page. Clinically significant abnormalities should also be recorded as relevant medical history/current medical condition.

The ECG parameters to be reported in the database will include:

- Date and time of ECG
- Heart rate
- PR interval
- QT interval
- QTc interval
- QTcF interval
- QRS duration

The overall interpretation will be collected with a Yes/No statement to confirm if any clinically significant abnormalities are present which need to be specified further.

Original ECG tracings, appropriately signed, will be archived at study site.

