7.1.5. Treatment of AEs

All AEs should be treated appropriately. Treatment may include one or more of the following: no action taken (ie, further observation only); study drug dosage adjusted/temporarily interrupted; study drug permanently discontinued due to this AE; concomitant medication given; non-drug

therapy given; subject hospitalized/subject's hospitalization prolonged. The action taken to treat the AE should be recorded on the Adverse Event Form.

Once an AE is detected, it should be followed until its resolution to baseline grade or better, or until it is judged to be stable or permanent by the investigator, or the participant withdraws consent. Assessment should be made at each visit (or more frequently, if necessary) of any changes in severity, the suspected relationship to the study drug, the interventions required to treat it, and the outcome.

Information about potential risks of the investigational drug will be included in the subject's informed consent and should be discussed with the subject as part of the informed consent signing and during the study as needed.

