9.3. Safety Analysis and Statistics

Safety will be evaluated by the following:

- Incidence and severity of AEs
- Results from measurements of vital signs
- Results from measurements of ECGs
- Physical evaluation
- Results from measurements for parameters of clinical laboratory tests (hematology, clinical chemistry, and urinalysis)

All vital signs, ECG, laboratory and AE data will be listed by subject and visit/time and, if ranges are available, abnormalities will be flagged and brought to the Investigator's attention for review. Summary statistics will be provided by visit/time.

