Hypophosphatemia	2.0 - 2.4 mg/dL	1.5 -1.9 mg/dL or replacement Rx required	1.0-1.4 mg/dL intensive Rx or hospitalization required	< 1.0 mg/dL or life- threatening arrhythmia
Hyperbilirubinemia	1.1 -1.5 x ULN	1.6-2.5 x ULN	2.6-5 x ULN	>5 x ULN
BUN	1.25-2.5 x ULN	2.6-5 x ULN	5.1- 10 x ULN	> 10 x ULN
Creatinine	1.1-1.5 x ULN	1.6-3.0 x ULN	3.1-6 x ULN	> 6 x ULN or required dialysis
URINALYSIS				
Proteinuria	1+or< 0.3% or <3g/L or 200 mg - 1 gm loss/day	2 -3 + or 0.3 - 1.0% or 3-10 g/L 1- 2 gm loss/day	4+or> 1.0% or> 10 g/L 2-3 5 gm loss/day	nephrotic syndrome or > 3 5 gm loss/day
Hematuria	microscopic only	gross, no clots	gross+ clots	obstructive or required transfusion
CARDIAC DYSFUNCTION				
Cardiac Rhythm		asymptomatic, transient signs, no Rx required	recurrent/persistent; No Rx required	requires treatment
Hypertension	transient inc. >20mm; no Rx	recurrent, chronic, > 20 mm, Rx required	requires acute Rx; No hospitalization	requires hospitalization
Hypotension	transient orthostatic hypotension, No Rx	symptoms correctable with oral fluids Rx	requires IV fluids; no hospitalization required	requires hospitalization
Pericarditis	minimal effusion	mild/moderate asymptomatic effusion, no Rx	symptomatic effusion; pain; ECG changes	tamponade; pericardiocentesis or surgery required
Hemorrhage, Blood Loss	microscopic/occult	mild, no transfusion	gross blood loss; 1-2 units transfused	massive blood loss; > 3 units transfused

WHO Toxicity Grading Scale for determining the severity of AEs, continued

ITEM	Grade 1 Toxicity	Grade 2 Toxicity	Grade 3 Toxicity	Grade 4 Toxicity
RESPIRATORY				
Cough	transient- no Rx	treatment associated cough local Rx	uncontrolled	
Bronchospasm, Acute	transient; no Rx < 80% - 70% FEV ₁ (or peak flow)	requires Rx normalizes with bronchodilator; FEV ₁ 50% - 70% (or peak flow)	no normalization with bronchodilator; FEV ₁ 25% - 50% (or peak flow retractions)	cyanosis: FEV ₁ < 25% (or peak flow) or intubated
GASTROINTESTINAL				
Stomatitis	mild discomfort; no limits on activity	some limits on eating/drinking	eating/talking very limited	requires IV fluids
Nausea	mild discomfort; maintains reasonable intake	moderate discomfort; intake decreased significantly; some activity limited	severe discomfort; no significant intake; activities limited	minimal fluid intake
Vomiting	transient emesis	occasional/moderate vomiting	orthostatic hypotension or IV fluids required	hypotensive shock or hospitalization required for IV fluid therapy

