Constipation	Mild	moderate	severe	distensions w/vomiting
Diarrhea	transient 3-4 loose stools/day	5-7 loose stools/day	orthostatic hypotension or > 7 loose stools/ day or required IV fluids	hypotensive shock or hospitalization for IV fluid therapy required
NEURO & NEUROMUSCULAR				
Neuro-Cerebellar	slight incoordination dysdiadochokinesis	intention tremor, dysmetria, slurred speech; nystagmus	locomotor ataxia	incapacitated
Mood	mild anxiety or depression	moderate anxiety or depression and therapy required	severe anxiety or depression or mania; needs assistance	acute psychosis; incapacitated, requires hospitalization
Neuro Control (ADL activities of daily living)	mild difficulty concentrating; no Rx; mild confusion/agitation; ADL unaffected	moderate confusion/agitation some limitation of ADL; minimal Rx	severe confusion/agitation needs assistance for ADL; therapy required	toxic psychosis; hospitalization
Muscle Strength	subjective weakness no objective symptoms/signs	mild objective signs/symptoms no decrease in function	objective weakness function limited	paralysis

WHO Toxicity Grading Scale for determining the severity of AEs, continued

ITEM	Grade 1 Toxicity	Grade 2 Toxicity	Grade 3 Toxicity	Grade 4 Toxicity
OTHER PARAMETERS				
FEVER: oral, >12 hours	37.7-38.5 C or 100.0-101.5 F	38.6-39.5 C or 101.6-102.9 F	39.6-40.5 C or 103-105 F	>40 C or >105 F
Headache	mild, no Rx therapy	transient, moderate, Rx required	severe, responds to initial narcotic therapy	intractable; required repeated narcotic therapy
Fatigue	no decrease in ADL	normal activity decreased 25-50%	normal activity decreased >50% can't work	unable to care for self
Allergic Reaction	pruritus without rash	localized urticaria	generalized urticaria; angioedema	anaphylaxis
Local Reaction	tenderness or erythema	induration < 10 cm or phlebitis or inflammation	induration > 10 cm or ulceration	necrosis
Mucocutaneous	erythema; pruritus	diffuse, maculopopular rash, dry desquamation	vesiculation, moist desquamation, or ulceration	exfoliative dermatitis, mucous membrane involvement or erythema, multiforme or suspected Stevens-Johnson or necrosis requiring surgery

13. APPENDIX 2 – PROTOCOL SUMMARY OF CHANGES, AMENDMENT 1

Rationale:

Updates were included to clarify that approved forms of birth control are not prohibited prescription medications.

The following amendments were incorporated:

Page	Section	17-Jan-2020, v1.0 WAS	21-Jan-2020, v2.0 IS
1	Title Page, Header	V1.0, 17-Jan-2020	V2.0, 21-Jan-2020

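### The required severity scale gives alkaline phosphatase at 1.6 to 2.5 x ULN two grades (and, if the original page confirms it, fever above 40.0 and up to 40.5 C), and no rule says which applies

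*Combined protocol and SAP*

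**What the plan says.** Section 7.1.1 names one scale for AE severity: "The World Health Organization (WHO) toxicity grading scale (see Section 12) will be used for assessing AE severity". It gives a fallback with a stated scope: "Table 2 will be used for assessing severity for AEs that are not specifically listed in the WHO toxicity grading scale". Section 7.3 refers severity back to 7.1.1. Section 9.3 makes "Incidence and severity of AEs" one of the safety evaluations.

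The chemistry panel in Section 6.4.4.2 includes "alkaline phosphatase, ALT, AST" but not GGT. Under Table 1, footnote 5, the panel is drawn at screening, before injection and at completion of imaging.

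Appendix 1 sets the grade limits. For alkaline phosphatase and GGT, Grade 1 is 1.25 to 2.5 x ULN and Grade 2 is 1.6 to 5 x ULN. For AST, ALT and BUN, Grade 1 is the same but Grade 2 is 2.6 to 5 x ULN. The fever row applies to oral fever lasting more than 12 hours. Its Grade 3 entry is "39.6-40.5 C or 103-105 F", and its Grade 4 entry is above 40 C or above 105 F.

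**The concern.** A mandatory severity scale should give one grade to each value. In these rows a higher grade begins before the lower one ends. Two people grading the same alkaline phosphatase AE at, say, 2.0 x ULN could record Grade 1 and Grade 2, and both would be following the protocol.

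Safety and tolerability is one of the two study objectives, and severity is one of its reported descriptors. With up to 6 evaluable subjects, a single event graded either way would visibly change the severity summary.

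**Working it through.** The plan states no figure to reproduce. The check is to intersect the grade bands within each row of Appendix 1 and then look for a tie-break.

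**Step 1. Liver enzymes and BUN (x ULN).** Overlap = Grade 1 upper limit minus Grade 2 lower limit; a positive result means double grading.

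- Alkaline phosphatase: 2.5 - 1.6 = 0.9, so 1.6 to 2.5 has two grades.
- GGT: 2.5 - 1.6 = 0.9, the same range.
- AST, ALT and BUN: 2.5 - 2.6 = -0.1, no overlap.

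The Grade 1 band is 2.5 - 1.25 = 1.25 wide, so the overlap takes up 0.9 / 1.25 = 72% of it. All five rows share their Grade 1, 3 and 4 limits and differ only in where Grade 2 starts.

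**Step 2. Fever, as printed.** F = 1.8 x C + 32.

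- Celsius: Grade 3 ends at 40.5 and Grade 4 starts above 40.0, so temperatures above 40.0 and up to 40.5 C meet both.
- In Fahrenheit that range runs from 1.8 x 40.0 + 32 = 104.0 F to 1.8 x 40.5 + 32 = 104.9 F. The Fahrenheit limits (103 to 105 F, then above 105 F) place all of it in Grade 3.
- The two Grade 4 limits disagree: 105 - 104.0 = 1.0 F, and 1.0 / 1.8 = 0.56 C. They are joined by an or, so neither settles the grade.

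**Step 3. Other rows.** The same check on amylase, bilirubin, creatinine, PT, APTT, and high sodium, potassium, calcium and glucose found no overlap. Two other rows share single endpoints: bronchospasm at 70% and 50% of FEV1, and proteinuria at 1 g/day. These are points, not ranges.

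**Step 4. Tie-break.** Table 2 covers only AEs that the scale does not list, and alkaline phosphatase, GGT and fever are all listed. Sections 7.1.1, 7.3, 7.4 and 9.3 and Appendix 1 contain no rule for a value that fits two grades.

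**Step 5. Could this be a text-extraction artefact?** The available text of Appendix 1 has lost characters elsewhere; the proteinuria row reads "2-3 5 gm loss/day". The 1.6 limit appears in two separate rows, so an artefact is unlikely there. The Grade 4 Celsius fever limit appears once, so it must be checked on the original page.

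**The case against.** The strongest case against is that this is a probable typographical slip with almost no reach.

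- GGT is not in the panel, so no planned test yields a value.
- The fever row needs more than 12 hours. Scheduled temperatures (screening, pre-injection, completion of imaging) cannot show that by themselves, and the printed limit is unverified.
- Alkaline phosphatase is drawn once after injection, at the end of imaging, in subjects screened for clinically significant laboratory abnormalities and given a single microdose.
- An abnormal value needs a grade only if it first qualifies as an AE under 7.1.1: symptomatic, clinically significant or needing therapy.
- Section 9.3 lists laboratory values and vital signs by subject, so the measurement stays visible whatever grade is recorded.

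All of this stands and makes the point minor. It does not remove the contradiction in a required scale for an analyte that the study measures.

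Two stronger readings are tempting, and the documents support neither.

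**Length of follow-up.** Section 7.1.5 says of an AE that "it should be followed until its resolution to baseline grade or better", so a reader might infer that follow-up depends on the grade chosen. Section 6.4.4, however, requires repeat laboratory evaluations until the result is normal or the change is no longer clinically relevant, and that rule uses no grades. From a normal baseline, return to baseline grade means falling below 1.25 x ULN, where nothing overlaps. For fever, an overlap between Grades 3 and 4 does not affect return to an afebrile baseline.

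**ECG findings.** Section 6.4.5 says "Clinically significant abnormalities should also be recorded as relevant medical history/current medical condition", and a reader might infer that ECG findings after injection bypass AE recording. Section 7.1.1 already makes clinically significant test results AEs and requires every AE to be recorded. The instruction in 6.4.5 adds a record and replaces none.

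**Conclusion.** The contradiction is real for alkaline phosphatase. As printed, Appendix 1 assigns both Grade 1 and Grade 2 to every value from 1.6 to 2.5 x ULN, and the plan gives no way to choose. The GGT row has the same fault but no planned measurements. The fever overlap, and the 1.0 F (0.56 C) disagreement between the Grade 4 limits, hold only if the original page confirms the Celsius limit.

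The consequence is confined to the AE severity grade reported under 9.3. AE incidence does not depend on it. The stopping rule in 5.2.4 turns on drug-related SAEs, the SAE definition in 7.1.2 uses no grades, and the liver AESI in 7.1.3 uses its own ALT, AST and bilirubin thresholds. Dosimetry is untouched. The documents give no basis for an expected number of affected events; in up to 6 evaluable healthy subjects given one microdose it is probably small. The point is minor, but the scale is wrong as written and should be corrected.

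This rests on the printed limits for alkaline phosphatase and GGT being as extracted. Confidence in that is high, because the same entry appears in both rows.

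**What to change.** Check the alkaline phosphatase, GGT and fever rows against the original page and the source scale. Then take one of two routes.

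1. Reconcile the alkaline phosphatase and GGT rows, and the fever row if confirmed, so that adjacent grades do not overlap and the Celsius and Fahrenheit limits agree. The sponsor settles which limits are right; this review does not.
2. If the source scale carries the same limits, add one sentence to 7.1.1 giving a single sponsor-chosen rule for any value that meets two grades. This would also cover the shared endpoints in the bronchospasm and proteinuria rows.

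The cost is two or three corrected table rows, or one sentence. No new data, visits or analyses are needed.

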7.1.2. SAE Definition

An SAE is defined as an event which:

- is fatal or life-threatening
- constitutes a congenital anomaly/birth defect

- results in persistent or significant incapacity or substantial disruption of the ability to conduct normal life functions
- is medically significant, ie, defined as an event that jeopardizes the subject or may require medical or surgical intervention to prevent one of the outcomes listed above
- requires in-patient hospitalization or prolongation of existing hospitalization, unless hospitalization is for:
 - routine treatment or monitoring of the studied indication, not associated with any deterioration in condition
 - elective or pre-planned treatment for a preexisting condition that is unrelated to the indication under study and has not worsened since the start of study drug

7.1.3. Adverse Events of Special Interest Definition

Adverse events of special interest (AESI) are required to be reported by the investigator to the Sponsor immediately (ie, no more than 24 hours after learning of the event; see Section 7.2 for reporting instructions). AESI for this study are as follows:

- Cases of potential drug-induced liver injury that include an elevated ALT or AST in combination with either an elevated bilirubin or clinical jaundice, as defined by Hy's Law
 The finding of an elevated ALT or AST (> 3 ULN) in combination with either an elevated total bilirubin (2 ULN) or clinical jaundice in the absence of cholestasis or other causes of hyperbilirubinemia is considered to be an indicator of severe liver injury (as defined by Hy's Law). Therefore, investigators must report as an AE the occurrence of either of the following:
 - Treatment-emergent ALT or AST > 3x ULN in combination with total bilirubin >2 x ULN
 - Treatment-emergent ALT or AST > 3 x ULN in combination with clinical jaundice

The most appropriate diagnosis or (if a diagnosis cannot be established) the abnormal laboratory values should be recorded on the Adverse Event eCRF and reported to the Sponsor immediately (ie, no more than 24 hours after learning of the event), either as a SAE or an AESI.

- Suspected transmission of an infectious agent by the study drug, as defined below
 Any organism, virus, or infectious particle (eg, prion protein transmitting transmissible spongiform encephalopathy), pathogenic or non-pathogenic, is considered an infectious agent. A transmission of an infectious agent may be suspected from clinical symptoms or laboratory findings that indicate an infection in a subject exposed to a medicinal product. This term applies only when a contamination of the study drug is suspected.

7.1.4. Cases of Accidental Overdose or Medication Error

Accidental overdose and medication error (hereafter collectively referred to as "special situations"), are defined as follows:

- Accidental overdose: accidental administration of a drug in a quantity that is higher than the assigned dose
- Medication error: accidental deviation in the administration of a drug
 - In some cases, a medication error may be intercepted prior to administration of the drug.

Special situations are not in themselves AEs but may result in adverse events. Each AE associated with a special situation should be recorded separately on the Adverse Event eCRF. If the associated adverse event fulfills seriousness criteria, the event should be reported to the Sponsor immediately (ie, no more than 24 hours after learning of the event; see Section 7.2). For [¹⁸F]GTP1, adverse events associated with special situations should be recorded as described below for each situation:

- Accidental overdose: Enter the adverse event term. Check the "Accidental overdose" and "Medication error" boxes.
- Medication error that does not qualify as an overdose: Enter the adverse event term. Check the "Medication error" box.
- Medication error that qualifies as an overdose: Enter the adverse event term. Check the "Accidental overdose" and "Medication error" boxes.

In addition, all special situations associated with [¹⁸F]GTP1, regardless of whether they result in an adverse event, should be recorded on the Adverse Event eCRF as described below:

- Accidental overdose: Enter the drug name and "accidental overdose" as the event term. Check the "Accidental overdose" and "Medication error" boxes.
- Medication error that does not qualify as an overdose: Enter the name of the drug administered and a description of the error (eg, wrong dose administered, wrong dosing schedule, incorrect route of administration, wrong drug, expired drug administered) as the event term. Check the "Medication error" box.
- Medication error that qualifies as an overdose: Enter the drug name and "accidental overdose" as the event term. Check the "Accidental overdose" and "Medication error" boxes. Enter a description of the error in the additional case details.
- Intercepted medication error: Enter the drug name and "intercepted medication error" as the event term. Check the "Medication error" box. Enter a description of the error in the additional case details.

As an example, an accidental overdose that resulted in a headache would require two entries on the Adverse Event eCRF, one entry to report the accidental overdose and one entry to report the headache. The "Accidental overdose" and "Medication error" boxes would need to be checked for both entries.

7.1.5. Treatment of AEs

All AEs should be treated appropriately. Treatment may include one or more of the following: no action taken (ie, further observation only); study drug dosage adjusted/temporarily interrupted; study drug permanently discontinued due to this AE; concomitant medication given; non-drug

therapy given; subject hospitalized/subject's hospitalization prolonged. The action taken to treat the AE should be recorded on the Adverse Event Form.

Once an AE is detected, it should be followed until its resolution to baseline grade or better, or until it is judged to be stable or permanent by the investigator, or the participant withdraws consent. Assessment should be made at each visit (or more frequently, if necessary) of any changes in severity, the suspected relationship to the study drug, the interventions required to treat it, and the outcome.

Information about potential risks of the investigational drug will be included in the subject's informed consent and should be discussed with the subject as part of the informed consent signing and during the study as needed.

